- Every two months, during the intervention process (six months), the ASP physician extracts the PHCC's lab- and diagnosis-linked prescription statistics for pharyngotonsillitis for the last two months. The statistics are presented in a doctor meeting or staff meeting to follow up on the action plan. This statistic is extracted for the PHCC as a whole and for each individual doctor to form the basis for self-reflection. Based on the result, the continued work is adjusted as needed and the ASP physician notes a summary in the PHCC's CRF.
- If questions arise during the intervention, the ASP physician can consult with Strama Västra Götaland.

The control group

PHCCs that are randomized to the control group do not receive any study-related active intervention and the doctor who is responsible for reporting antibiotic prescription statistics to Strama at these PHCCs do not receive the above mentioned ASP training. The PHCCs in the control group, like all other PHCCs in Västra Götaland, participate in the activities that Strama Västra Götaland carries out regardless of this project.

Data collection

Collected data for all PHCCs (intervention group + control group)

The following data is collected for all PHCCs, both in the intervention group and the control group; at the start of the study (when the intervention starts at the PHCCs = baseline), as well as 6, 12 and 18 months after the date when the PHCCs in the intervention group begin the intervention with reflective meetings around pharyngotonsillitis.

Quality indicators for pharyngotonsillitis - measurement period last six months:

- the proportion of patients prescribed antibiotics (J01 excluding methenamine) for pharyngotonsillitis having a positive rapid test for GAS
- the proportion of patients prescribed antibiotics (J01 excluding methenamine) for pharyngotonsillitis having a negative rapid test for GAS
- the proportion of patients prescribed antibiotics (J01 excluding methenamine) for pharyngotonsillitis given first line antibiotics (PcV) according to the national Swedish guidelines
- the proportion of positive rapid test for GAS of all analysed rapid test for GAS among patients with a formal diagnosis of pharyngotonsillitis
- the proportion of patients with a formal diagnosis of pharyngotonsillitis where CRP was analysed
- the proportion of patients with a formal diagnosis of pharyngotonsillitis where throat swab culture was analysed

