- the proportion of patients with a formal diagnosis of pharyngotonsillitis where a rapid test for mononucleosis has been analysed

This data is extracted (for the last six months) using the software "Medrave4 Primary care ®" at baseline and after 6, 12 and 18 months. Virtually all PHCCs in Västra Götaland have this software and regularly use it for monitoring quality at the PHCC. In addition, all PHCCs included in this project will check that the rapid test for GAS is registered in the electronic medical record in such a way that the software "Medrave4 Primary Care ®" can identify this.

Structural data required in CRF:

- Staffing at the present time: Number of permanent-employed GPs, Residents, interns, and locum tenens, respectively divided into short-term (<3 months of service) and long-term (\geq 3 months of service) locum tenens.
- The number of patients with pharyngotonsillitis per 1000 patients enlisted at the PHCC at baseline.

Structural data for each participating PHCC

These are obtained from Munin (a quality monitoring software for Primary care in Västra Götaland):

- Type of PHCC: run privately or public?
- the size of the PHCC (number of enlisted patients) and age profile of enlisted patients?
- geographical location (large or mid-sized city versus small village)?
- the number of patients with pharyngotonsillitis per 1000 enlisted patients and year?
- Adjusted Clinical Group (ACG); a measure for evaluating the enlisted population's state of health)?
- Care-need index (CNI); socio-economic index of patients enlisted at the PHCC

Data processing

Descriptive statistics

Descriptive statistics (a measure of central tendency and probability distribution) will be presented for the all previously stated research questions at the start of the study (when the intervention starts at the PHCCs = baseline) and after 6, 12 and 18 months.

Comparisons at baseline

Comparative statistics (chi-two tests and t-tests pending on variable type) will be performed to identify differences between the intervention group and the control group at baseline.

Estimation of change

Any change between the data for the 6 months prior to the intervention (when the intervention starts at the PHCCs = baseline) and measurement after 6, 12 and 18 months, respectively, is calculated for each PHCC regarding the following outcome measures:

Primary outcome measure

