1. the proportion of patients with antibiotic-treated (J01 excluding methenamine) pharyngotonsillitis having a positive rapid test for GAS

Secondary outcome measures

2. the proportion of patients with pharyngotonsillitis and a negative rapid test for GAS prescribed antibiotics (J01 excluding methenamine)
3. the proportion of antibiotic-treated (J01 excluding methenamine) patients with pharyngotonsillitis treated with recommended antibiotic according to guidelines (PcV)
4. the proportion with pharyngotonsillitis diagnosis where CRP was analysed
5. the proportion of patients with pharyngotonsillitis prescribed antibiotics where no throat swab was taken
6. the proportion with pharyngotonsillitis diagnosis where throat swab culture was analysed
7. the proportion with pharyngotonsillitis diagnosis where a rapid test for mononucleosis has been analysed.

Regression analysis

A) Investigate if the intervention is effective

To investigate whether a change in outcome measure 1-4 differs between the intervention group and the control group, linear regression is performed where adjustment is made for any variables that differ at baseline. A regression is performed for each individual outcome measure at follow-up after 6, 12 and 18 months. Change in the respective outcome measures compared to baseline is used as a dependent variable. Group affiliation (intervention group or control group) will be used as an independent variable. Independent variables will also be the following covariates taken from baseline measurement: the number of enlisted patients at baseline, location in cities versus small villages, Adjusted Clinical Group (ACG), Care-need index (CNI) and type of PHCC (private/public).

B) Investigate if structural factors are associated with maintaining the effect of the intervention

To study if there is a relationship between more permanent change in the proportion of patients with antibiotic-treated (J01 excluding methenamine) pharyngotonsillitis who had a positive rapid test for GAS (primary outcome measure) and structural data in the intervention group, regression analysis will be done.

Change between baseline and follow-up data (18 months after initiation of intervention) for the proportion of patients treated with antibiotics for pharyngotonsillitis who have had a positive rapid test for GAS is used as a dependent variable. The following independent variables will be used:

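### The collection list records the RADT-negative share of treated patients, but secondary outcome 2 is the treated share of RADT-negative patients, and the listed proportions do not determine it

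*Combined protocol and SAP*

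**What the plan says.** The combined protocol and SAP describes this quantity in two ways.

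- **Data collection, Quality indicators for pharyngotonsillitis, second item:** "the proportion of patients prescribed antibiotics (J01 excluding methenamine) for pharyngotonsillitis having a negative rapid test for GAS". It is worded like the first item, "the proportion of patients prescribed antibiotics (J01 excluding methenamine) for pharyngotonsillitis having a positive rapid test for GAS", which matches the primary outcome. Both are shares of antibiotic-treated patients.
- **Research questions, item 2, and Secondary outcome measures, item 2:** "the proportion of patients with pharyngotonsillitis and a negative rapid test for GAS prescribed antibiotics (J01 excluding methenamine". Here the denominator is patients with a negative RADT.

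The fourth indicator is the only other listed RADT item: "the proportion of positive rapid test for GAS of all analysed rapid test for GAS among patients with a formal diagnosis of pharyngotonsillitis".

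Outcome 2 is among those tested. Under Regression analysis, part A: "To investigate whether a change in outcome measure 1-4 differs between the intervention group and the control group, linear regression is performed", with a separate regression at 6, 12 and 18 months. Under Descriptive statistics: "Descriptive statistics (a measure of central tendency and probability distribution) will be presented for the all previously stated research questions", at baseline and at each follow-up.

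On the source of the indicators: "This data is extracted (for the last six months) using the software" that the centres already use for quality monitoring. The plan lists proportions. It does not list the number of patients treated, tested or RADT-negative.

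**The concern.** The two definitions condition in opposite directions. The indicator is P(RADT-negative | treated); the outcome is P(treated | RADT-negative). Outcomes 1, 3 and 4 each have a matching indicator, so outcome 2 is the only tested outcome without one.

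Outcome 2 is the tested measure that looks directly at prescribing after a negative test. The indicator depends as well on how many positive and untested patients are treated. Less prescribing without a test is a change the programme would welcome, since the Background makes a positive RADT the normal condition for antibiotics. That change shrinks the indicator's denominator and pushes the indicator up, which would look like a worsening. Because it would occur mainly in one arm, randomization would not remove it. A shift in GAS prevalence common to both arms should largely cancel, and this point does not rely on one.

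**Working it through.** The plan gives no figure for this quantity, so there is none to reproduce. All counts below are assumed.

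**1. Can outcome 2 be recovered from the listed proportions?** Assume one RADT per tested patient. Let I1, I2 and p be the first, second and fourth indicators, and f the share of RADT-positive patients who are treated.

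- Total treated = f × positives / I1
- Treated negatives = I2 × total treated
- Outcome 2 = treated negatives / negatives = f × (I2/I1) × p/(1−p)

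No listed item gives f. Setting f = 1 gives only an upper bound.

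**2. Two centres, each with 60 RADT-positive and 200 RADT-negative patients**

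| | Centre A | Centre B |
|---|---|---|
| Treated: positive / negative / untested | 60 / 40 / 20 | 45 / 30 / 15 |
| Total treated | 120 | 90 |
| I1 | 60/120 = 50% | 45/90 = 50% |
| I2 | 40/120 = 33.3% | 30/90 = 33.3% |
| p | 60/260 = 23.1% | 60/260 = 23.1% |
| f | 60/60 = 1.00 | 45/60 = 0.75 |
| Outcome 2 | 40/200 = **20%** | 30/200 = **15%** |

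Formula check: A, 1.00 × (40/60) × (60/200) = 0.20; B, 0.75 × (30/45) × (60/200) = 0.15.

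A second set gives the same answer. Take three centres with 200 diagnosed patients each:

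- 50 positive and 50 negative tests, treating 40 / 10 / 10 (positive / negative / untested): outcome 2 = 10/50 = 20%.
- The same tests, treating 20 / 5 / 5: 5/50 = 10%.
- 80 positive and 80 negative tests, treating 40 / 10 / 10: 10/80 = 12.5%.

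All three have I1 = 66.7%, I2 = 16.7% and p = 50%. Because the number diagnosed is the same, the one listed count-type item on these patients (cases per 1000 enlisted) does not help.

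**3. What if I2 were analysed as outcome 2?** Start from A, with 60 treated positives and 200 negatives held fixed.

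| Treated negatives | Treated untested | Outcome 2 | I2 |
|---|---|---|---|
| 40 (start) | 20 | 20% | 40/120 = 33.3% |
| 38 | 10 | 38/200 = 19% | 38/108 = 35.2% |
| 35 | 10 | 35/200 = 17.5% | 35/105 = 33.3% |
| 30 | 10 | 30/200 = 15% | 30/100 = 30% |
| 20 | 20 | 20/200 = 10% | 20/100 = 20% |

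Against an unchanged control arm, the second row gives a difference in change of −1.0 point on outcome 2 and +1.9 points on I2. In the third row a real improvement of 2.5 points leaves I2 flat. In the last two rows both measures fall.

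In the second row, suppose the 10 untested patients are tested instead, with 23.1% positive, all positives treated and 19% of negatives treated. Positives become 62.31, negatives 207.69 and treated negatives 0.19 × 207.69 = 39.46. I2 is then 39.46/(62.31 + 39.46 + 10) = 35.3%, so the direction is unchanged.

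**4. When do the directions differ?** With P treated positives fixed, N treated negatives and U treated untested patients, I2 rises if N′/N > (P+U′)/(P+U). For untested prescribing halved and P = 60:

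- U 20 to 10: 70/80 = 0.875, so I2 rises only if treated negatives fall by less than 12.5%.
- U 6 to 3: 63/66 = 0.955, limit 4.5%.
- U 36 to 18: 78/96 = 0.8125, limit 18.8%.

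**The case against.** The best reply is that the outcome is clearly defined and the collection list is only a summary. Research question 2 and secondary outcome 2 agree, the regression uses the outcome measures, and nowhere does the plan say that the indicator will be analysed instead. The list is visibly incomplete, since outcome 5 ("the proportion of patients with pharyngotonsillitis prescribed antibiotics where no throat swab was taken") has no item either. Denominators are loose elsewhere too: research question 3 reads as a share of all pharyngotonsillitis patients, outcome 3 as a share of those treated.

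The counts needed also underlie the indicators. Treated negatives are the numerator of the second indicator; with one test per patient, negatives are the denominator minus the numerator of the fourth. If counts are kept, outcome 2 can be computed. Failing that, if f is stable and similar between arms, the listed proportions fix outcome 2 up to a constant factor. Opposite movement needs a fairly specific pattern.

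Much of this stands. The regression is not at fault, the harm is conditional, and the counts may be exportable. But the plan names proportions as the data to collect and never says that numerators and denominators are kept. The route through the second and fourth indicators is not described, and an assumption about f is not stated. An incomplete list is a reason to complete it. Here it is not merely silent: it contains a near-duplicate of outcome 2 that could be substituted unnoticed.

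**Conclusion.** The concern holds. Data collected as listed yield a different measure from the one tested as secondary outcome 2, and the listed proportions do not determine that outcome. Both conclusions are firm: the first follows from the wording, the second from the formula, given one RADT per tested patient.

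The practical effect is much less certain. It depends on whether counts are exported and on how far untested prescribing falls in one arm only. On the assumed counts, centres with identical indicators differ by 5 points on outcome 2. Opposite signs arise only when treated negatives fall by less than about 5% to 19% while untested prescribing halves; if only treated negatives fall, the two measures agree in direction. One secondary outcome is affected. The primary outcome is not, because its indicator matches its definition. This should be corrected, but it does not threaten the design.

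**What to change.** In the Data collection list add, for each centre and each six-month window:

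- (a) the number of pharyngotonsillitis patients with a negative RADT;
- (b) the number of those prescribed a J01 antibiotic other than methenamine.

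State that outcome 2 is computed as b/a.

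Keep the existing second indicator as descriptive. Together with the first it is the only listed route to the share treated without a RADT, 1 − I1 − I2 (in centre A, 1 − 0.500 − 0.333 = 0.167 = 20/120).

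The cost is two counts in the extraction template, from the same records and software, provided the tool exports them; confirm that before baseline extraction. No indicator is removed and no outcome is redefined.

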A randomized controlled trial to investigate whether a multifaceted Antimicrobial Stewardship Program can improve adherence to guidelines for diagnosis and treatment of uncomplicated pharyngotonsillitis in primary care

Abstract

Background: In order to achieve a rational use of antibiotics and slow down the development of antibiotic-resistant bacteria, it is important to develop and scientifically evaluate Antimicrobial Stewardship Programs (ASP), the purpose of which is to reduce unnecessary use of antibiotics. Pharyngotonsillitis (sore throat) is one of the most common causes of antibiotic prescription in primary care. Since adherence to guidelines on diagnosis and treatment of pharyngotonsillitis is insufficient, a well-defined, repeatable and scientifically evaluated ASP needs to be developed for this purpose.

Aims and objectives: To develop an ASP for pharyngotonsillitis and evaluate whether this intervention can increase compliance with guidelines for the diagnosis and treatment of pharyngotonsillitis in primary care.

Study Methods: A randomized controlled trial in which 50 primary health care centres (PHCCs) in Västra Götaland are randomized either to an intervention group implementing the newly developed ASP for pharyngotonsillitis or to a control group.

The intervention lasts for six months, including both doctors and nurses and involving reflective meetings on guidelines, didactic patient cases, identification of local improvement opportunities, the establishment of an action plan and recurrent feedback in the form of a lab- and diagnosis-linked prescription statistic for pharyngotonsillitis.

Antibiotic prescription for pharyngotonsillitis is followed up in relation to a rapid antigen detection test (RADT) for group A streptococci (GAS). Primary outcome measure: the proportion of patients with antibiotic-treated pharyngotonsillitis who have a positive RADT for GAS. Change in outcome measures will be compared between the control group and the intervention group at 6, 12 and 18 months.

Expected Results: If the trial shows that this ASP leads to increased adherence to guidelines for pharyngotonsillitis, the implementation of this ASP could lead to more rational use of antibiotics.

Background

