Antibiotic-resistant bacteria are becoming more common and constitute one of the biggest threats to our future health [1, 2]. To slow down this development, it is important not to prescribe antibiotics unnecessarily [3]. Pharyngotonsillitis (sore throat) is one of the most common causes of antibiotic prescribing in primary health care centres (PHCCs) [4, 5]. In the clinical everyday life, general practitioners (GPs) experience uncertainty about the treatment of patients with pharyngotonsillitis [6], and adherence to guidelines on diagnostics and treatment of pharyngotonsillitis needs to be improved [4, 7]. The single most important rule-of-thumb in primary care is to normally only prescribe antibiotics for pharyngotonsillitis when a positive rapid antigen detection test (RADT) for beta-haemolytic streptococci group A (GAS) is presented [8, 9].

It is important for GPs to have the opportunity to reflect on their own antibiotic prescribing, to have regular interdisciplinary discussions at the PHCC about antibiotics and guidelines to increase knowledge and understanding of the guidelines and thus feeling confident in the clinical everyday life [10-14]. Structural factors at the PHCC such as the manager's involvement and nurses' work on telephone counselling and on triage reception are also important in achieving a rational use of antibiotics [10]. Antimicrobial Stewardship Programs (ASP) are structured multifaceted interventions to reduce unnecessary antibiotic use and have in many cases led to more rational use of antibiotics within inpatient care [15-17]. There is largely no evidence showing which ASPs are effective in PHCCs, at least from a Swedish perspective since we have a comparatively low rate of antibiotic prescribing [17, 18]. Since pharyngotonsillitis is common and adherence to guidelines is insufficient, there is a need for a well-described, repeatable and scientifically evaluated ASP for pharyngotonsillitis.

Aims and Objectives

To scientifically develop and evaluate an ASP to see if this intervention can increase adherence to guidelines for the diagnosis and treatment of pharyngotonsillitis in primary care.

Research questions

Is there a difference between PHCCs randomized to ASP intervention or control in change from baseline and measurements after 6, 12 and 18 months regarding the following outcomes:

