- The PHCC has a license for the data extraction tool MedRave Primary Care.

Exclusion criteria:

- Newly opened PHCCs that have been in existence for less than one year (excluded because reliable measurement cannot be made at baseline)

Calculation of sample size (power calculation)

Assuming linear regression where the independent variable is the group affiliation (control or intervention), an effect size (Cohen's d) of 0.3, a significance level of 0.05 and a power of 0.95. Under these assumptions, 45 primary care centres are required. In order to have a safety margin, we will strive to include 50 primary care centres.

Study Design

PHCCs randomized to the intervention group

Any PHCC in Region Västra Götaland, Sweden, are required to have a dedicated contact GP to Strama Västra Götaland in order to be eligible for public funding: “The PHCC must have knowledge of current antibiotic resistance data, its adherence to treatment guidelines for infections in primary care and antibiotic prescription. The primary care centre must also appoint ASP physicians who cooperate with, and together with the operations manager, report to Strama Västra Götaland in these areas.”

These physicians, who already have a deep understanding of the issues around antibiotic stewardship, will be responsible for the ASP on their respective PHCC (called “ASP physicians”).

In order to be able to carry out the intervention, the ASP physicians at the PHCCs randomized to the intervention will receive training to lead workshops about diagnosis and treatment of pharyngotonsillitis at their PHCC. The workshops will include a Powerpoint presentation on current guidelines for pharyngotonsillitis, a discussion on a case study of pharyngotonsillitis with didactic questions and a tutor manual, present lab- and diagnosis-linked prescribing statistics of pharyngotonsillitis to their colleagues at the PHCC, to identify areas of potential improvement and to create an action plan based on this, which is then followed up at the PHCC as described below. Strama prepares and provides all the required materials for these workshops. The PHCCs' ASP physicians are trained during the month before the intervention commenced and the training will be held by the project manager and Strama Västra Götaland. Several training opportunities will be offered so that all ASP physicians at the PHCCs in the intervention group will be able to attend the training.

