the number of patients with pharyngotonsillitis per 1000 enlisted patients and year, the proportion of PHCCs located in cities versus small villages, Adjusted Clinical Group (ACG), Care-need index (CNI) and type of PHCC: (private/public), at baseline.

Expected results and significance

This study is expected to shed light on whether a well-defined ASP intervention can increase adherence to guidelines for the diagnosis and treatment of pharyngotonsillitis in primary care. If so, the implementation of this ASP could lead to improved diagnostics and more rational use of antibiotics in pharyngotonsillitis in primary care. In order to be able to slow down the increasing trend with an increasing proportion of resistant bacteria, it is important to avoid unnecessary antibiotic treatments.

The intervention will be well described so that it can be repeated elsewhere if the evaluation shows that the intervention is effective. The planned intervention is time-efficient in that the Strama group educates one ASP physician from each PHCC so that they, in turn, carry out the intervention at their respective PHCC.

References

2. WHO: **The evolving threat of antimicrobial resistance - Options for action**. Geneva: World Health Organization; 2012.
3. Davies J, Davies D: **Origins and evolution of antibiotic resistance**. *Microbiol Mol Biol Rev* 2010, **74**(3):417-433.

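### The single primary outcome is tested at 6, 12 and 18 months at an unadjusted 0.05, and nothing says which result decides whether the programme works

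*Combined protocol and SAP*

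**What the plan says.** The Abstract and the Primary outcome measure entry under Estimation of change define one primary outcome. Neither attaches a time to it.

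Three places list the follow-up times, and none ranks them:
- Abstract, Study Methods: "Change in outcome measures will be compared between the control group and the intervention group at 6, 12 and 18 months".
- Research questions, opening sentence: "Is there a difference between PHCCs randomized to ASP intervention or control in change from baseline and measurements after 6, 12 and 18 months".
- Regression analysis, part A, the analysis of whether the intervention is effective: "A regression is performed for each individual outcome measure at follow-up after 6, 12 and 18 months".

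The only error rate is in the sample size section, "a significance level of 0.05 and a power of 0.95", and it is attached to no time point.

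The plan speaks of a single overall answer. The Abstract's Expected Results begin "If the trial shows that this ASP leads to increased adherence to guidelines for pharyngotonsillitis". The section Expected results and significance says the intervention will be described so that "it can be repeated elsewhere if the evaluation shows that the intervention is effective".

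One time point is singled out in one place only. Part B, headed "Investigate if structural factors are associated with maintaining the effect of the intervention", uses change to 18 months. It is confined to the intervention group, so it makes no comparison with control.

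**The concern.** Three tests answer one question, and the plan does not say how three p-values become one answer. If they agree, nothing is lost. If they disagree, the plan gives no basis for a conclusion, and whoever writes the report can choose the deciding time with the results in view. The stated 0.05 would then no longer describe the error rate of the main conclusion.

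Disagreement is a realistic prospect. Each extraction covers the preceding six months ("This data is extracted (for the last six months) using the software") and the programme lasts six months. The three windows are therefore months 0-6 (during delivery), 6-12 (just after) and 12-18 (later). Part B's interest in whether an effect is maintained shows that the authors allow for these windows to differ.

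**Working it through.** **Plan's own figure.** The plan states no error rate for the three tests together, so there is none to reproduce. The starting point is its 0.05 per test. It does not say one-sided or two-sided; two-sided is assumed below.

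**Inputs from the protocol**
- Tests of the primary outcome: 3 (Regression analysis, part A).
- Level: 0.05 (sample size section).
- PHCCs: 50, taken as 25 per group (equal allocation assumed).
- Dependent variable: change from the same baseline at each time (Regression analysis, part A).

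**Input not in the documents.** The correlation ρ between the three change scores is not given. It is assumed, and varied from 0 to 0.9.

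**Step 1: independent tests (upper bound)**
- Any of three significant, two-sided: 1 − (1 − 0.05)³ = 1 − 0.857375 = 0.1426, or 14.3%.
- Any of three significant in the programme's favour (0.025 per test): 1 − (1 − 0.025)³ = 0.0731, or 7.3%.

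**Step 2: correlated tests.** Simulated t-tests on change scores, 25 against 25 PHCCs, no true effect, 400,000 trials per row. The last column is the chance that Holm's procedure rejects at any time. With no true effect this equals the chance that the smallest p-value is below 0.05/3 = 0.0167.

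| Assumed ρ | Any time, two-sided | Any time, favourable | All three significant | Holm, any rejection |
|---|---|---|---|---|
| 0 | 14.3% | 7.3% | 0.0% | 4.9% |
| 0.5 | 12.6% | 6.3% | 0.3% | 4.5% |
| 0.8 | 9.9% | 4.9% | 1.4% | 3.6% |
| 0.9 | 8.4% | 4.2% | 2.2% | 3.0% |

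A large-sample normal calculation agrees: 14.3%, 12.5%, 9.8% and 8.3% for the first column. At ρ = 0.95 it gives 7.3%, so 8% is the value at ρ of about 0.9 and not a floor.

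**Step 3: sidedness.** If the plan means one-sided 0.05 tests, the any-time rate is 14.2%, 11.8% and 8.0% at ρ = 0, 0.5 and 0.9. The conclusion is unchanged.

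**Step 4: effect of the decision rule**
- One time named in advance: 5%.
- Three separate questions, each with its own conclusion: 5% for each.
- All three required: at most 2.2% in the table.
- Any one suffices: 8-14%.

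The plan does not say which of these rules applies.

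**The case against.** The strongest reply is that the inflated rate belongs to a rule the plan never states. The research questions ask about change at each time and the windows do not overlap, so a natural reading is three time-specific answers, each at 0.05 with its own 5% error rate. All three regressions are pre-specified with one outcome and one set of listed covariates, so full reporting would show any selective emphasis.

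Much of this stands. What is shown is an undefined decision rule, and the inflation is conditional on one way of filling the gap. Full reporting does limit selective reporting. It does not say what to conclude from mixed results, and the plan still speaks of one verdict without tying it to any of the three answers.

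A reader might also suppose that 18 months is implied by part B. That analysis relates structural factors to change within the intervention group only, so it cannot settle a comparison with control.

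Three stronger readings are tempting and are not supported:
- **That the false-positive rate is in fact inflated.** This holds only under the any-one rule, which is not written.
- **That the shared baseline fixes the rate within a narrow band.** Take a stable PHCC level plus independent noise in each window, with baseline noise variance v times that at follow-up. Then ρ = v/(v + 1). Equal noise gives 0.5 and about 12.5%; v = 4 gives 0.8 and 9.8%; v = 0.5 gives 0.33 and 13.5%. Adjusting for the baseline outcome, which the plan's adjustment for variables that differ at baseline could bring in, gave 13.0-14.0% in simulated regressions with equal correlation between windows. The documents supply no variances or correlations, so only the wide range is defensible.
- **That roll-out is formally tied to this test.** The closing sections express a hope that the programme can be repeated if it works. They set out no adoption rule.

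**Conclusion.** The point holds as a missing decision rule for the primary outcome: three unadjusted 0.05 tests, one question, and no statement of which result answers it. That defect needs no simulation and cannot be repaired credibly once results are known.

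Its size is conditional. If significance at any one time were taken as proof of effectiveness, the two-sided error rate would be about 8-14% rather than 5%, and about 4-7% rather than 2.5% in the programme's favour. Both ranges rest on assumed correlations of about 0.9 down to 0. Under separate questions, or a requirement that all three be significant, there is no inflation.

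**What to change.** Before analysis, add one or two sentences to Regression analysis, part A. There are two workable forms.

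1. **One primary time.** Name one time point for outcome 1, give the reason, test it at 0.05 and make the other two secondary. Twelve months is defensible because its window lies wholly after delivery and covers the same calendar months as baseline. Eighteen months is defensible as a test of durability. The choice is the sponsor's.
2. **Holm across the three.** If an effect at any of the three times is to be claimable, pre-specify Holm for outcome 1: the smallest p-value against 0.05/3 = 0.0167, the next against 0.025, the last against 0.05.

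Neither needs extra data. Under the first, a result significant only at a non-primary time is not confirmatory. Under the second, some power is lost at each time because the first step tests at 0.0167, and Holm is somewhat conservative when the change scores are correlated (actual error rate 4.9% at ρ = 0, 3.0% at ρ = 0.9).
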